Comparative Effects of Blood Flow Restriction and Traditional Strength Training on Proximal Shoulder Musculature: A Randomized Clinical Trial

Approved by the ethics committee of Instituto Politécnico de Saúde do Norte (31/CE-IPSN/2024).

April 2024

STUDY OBJECTIVES

This study compared a 4-week blood-flow-restriction (BFR) resistance-training program performed at 30% of one-repetition maximum (1RM) with traditional high-load strength training at 70% of 1RM on shoulder muscle strength, power, endurance, and hypertrophy in healthy adults.

STUDY DESIGN

Parallel-group randomized controlled trial with two intervention arms: an experimental BFR group ($n = 12$; 3 men, 9 women) and an active comparator high-load group ($n = 11$; 3 men, 8 women; one dropout). All participants provided written informed consent in accordance with the Declaration of Helsinki.

PARTICIPANTS AND RECRUITMENT

Healthy volunteers were recruited via social media, discussion groups, and physical postings at CESPU facilities. Individuals of both sexes were eligible because prior work indicates comparable metabolic responses to BFR across genders. Eligibility was screened using an online questionnaire covering demographics, sport participation, and medical history. Eligible respondents were contacted by email to schedule baseline testing.

Eligibility Criteria

Inclusion criteria

- Age 18–40 years
- Body mass index (BMI) 18.5–30 kg/m² (individuals with obesity are commonly excluded due to higher cardiovascular, respiratory, and rheumatologic risk)

Exclusion criteria

- Participation in sports that heavily use the dominant arm (e.g., tennis, volleyball, handball)
- Current upper-limb strength training
- History of trauma or surgery involving the dominant upper limb

- Acute or chronic shoulder pain or radiating pain
- Cervical disc herniation or prior cervical surgery
- Upper-limb edema
- History of deep-vein thrombosis or oncologic/metabolic disease
- Pregnancy
- Persistent symptoms during training: numbness, tingling, or pain >7/10 on a numeric rating scale (BFR group criterion)
- Missing more than one training session

Randomization was performed with Sealed Envelope™.

METHODS

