Before data collection, the research team completed a familiarization phase to standardize equipment use, test administration, training procedures, and safety protocols. Responsibilities were assigned to specific team members, and minor adjustments were implemented as needed to ensure consistency and measurement accuracy.

Outcome assessments were performed after a standardized warm-up and always in the same sequence: Arm Circumference, Single-Arm Seated Shot-Put Test, Vertical Lift Strength, and Shoulder Endurance Test. Measurements were obtained at baseline (M0) and at least 24 h after the final training session (M1). Participants were instructed to avoid strenuous upper-limb activity for 24 h before testing.

Data-Collection Procedures

Arm Circumference: Circumference at the axillary level of the dominant arm was used as a proxy for deltoid muscle mass. With the participant at rest, three measurements were taken using a standard tape; the mean value was analyzed.

Single-Arm Seated Shot-Put Test (SASSPT): To assess shoulder power and upper-limb function, participants sat with trunk and shoulders against a wall, lower limbs extended, and the non-tested arm resting on the ipsilateral thigh to minimize compensation. Using a 4-kg medicine ball, participants performed maximal throws. Distances were recorded using floor tape; throws were video recorded to confirm first contact points. Three trials were performed; the mean distance was analyzed.

Vertical Lift Strength. Isometric strength for a vertical-lift task was measured with the Smart Groin Trainer (NeuroExcellence, Braga, Portugal). Participants were seated with the shoulder at 60° abduction and the elbow flexed; force was applied in the direction of vertical arm elevation. Three trials were performed; the best value was analyzed.

Shoulder Endurance. The Shoulder Endurance Test (SET) was used for its controlled cadence. Participants stood with their back against a wall, the contralateral heel touching the wall, and the ipsilateral leg positioned forward. The movement consisted of shoulder abduction to 90° with external rotation to 90° while touching the wall. Resistance was provided by a red elastic band; the hand-to-anchor distance was fixed at 1 m. A metronome guided cadence, starting at 60 bpm and increasing by 30 bpm every 20 s up to 150 bpm. The test ended when cadence or movement quality could not be maintained. Time to termination (seconds) was recorded.

Training Protocol

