Analyses were performed in SPSS version 29.0 (SPSS Inc., Chicago, IL, USA). Quantitative variables are presented as mean \pm SD or median (interquartile range), as appropriate. Between-group comparisons used Fisher's exact test, the Mann-Whitney U test, or independent-samples t tests. Within-group pre- to post-changes were evaluated with paired-samples t tests. For significant outcomes, Cohen's d was calculated and interpreted as: very small, $0.01 < d \leq 0.20$; small, $0.20 < d \leq 0.50$; moderate, $0.50 < d \leq 0.80$; large, $0.80 < d \leq 1.20$; very large, $1.20 < d \leq 2.00$; and huge, $d > 2.00$. Statistical significance was set at $p < 0.05$.

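### The between-group tests are not tied to baseline, follow-up or change, and none adjusts for the baseline value already measured

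*Combined protocol and SAP*

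**What the plan says.** The Study Objectives section makes the question a comparison of two programmes: "This study compared a 4-week blood-flow-restriction (BFR) resistance-training program" with a high-load programme. Study Design describes a "Parallel-group randomized controlled trial with two intervention arms", with 12 participants in the BFR arm and 11 in the high-load arm, the latter noted as "3 men, 8 women; one dropout".

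Under Methods, four outcomes are assessed, "always in the same sequence: Arm Circumference, Single-Arm Seated Shot-Put Test, Vertical Lift Strength, and Shoulder Endurance Test". Each is measured at baseline (M0) and again at least a day after the last session (M1).

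The Statistical Analysis section compares the arms with Fisher's exact test, "the Mann-Whitney U test, or independent-samples t tests". No time point, change score or covariate is attached to these tests. The next sentence is the only one that mentions change: "Within-group pre- to post-changes were evaluated with paired-samples t tests". The documents contain no ANCOVA, mixed model, group-by-time term or other adjustment for M0.

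**The concern.** The analysis that answers the objective is not defined. The sentence on group comparisons fits three readings:

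- **Tests at M0 only.** The post-training comparison of the arms then has no test. Two separate paired tests remain, and a significant change in one arm beside a non-significant change in the other does not show that the arms differ.
- **Tests at M1.** The baseline values are collected but not used in comparing the arms.
- **Tests on M1 − M0.** The baseline is used, but with its coefficient fixed at 1 whatever the data say.

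Three things are at stake: error control if the choice between M1 and change is left open, power in a trial of about 23 people, and how to read the result when the arms happen to differ at baseline. The last is a practical matter at this size, because sizeable chance imbalances are common.

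**Working it through.** **Inputs.** From the documents: 12 and 11 participants, four outcomes at M0 and M1, significance level 0.05 (taken as two-sided). The documents give no target effect, SD, M0–M1 correlation or power, so there is no stated figure to reproduce. Assumed: normal data, a true difference of 0.8 SD at M1, correlation *r*, and *s* = SD(M1)/SD(M0).

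**1. Precision.** In M1 SD units, k = √(1/12 + 1/11) = 0.4174. The standard errors of the group difference are:

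- M1 only: k
- change: k·√(1 + 1/s² − 2r/s)
- ANCOVA: k·√((1 − r²)·20/19), where 20/19 is the average price of estimating the M0 slope

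At r = 0.7 and s = 1:

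- M1 only: 0.417
- change: 0.4174 × √0.60 = 0.323
- ANCOVA: 0.4174 × √(0.51 × 20/19) = 0.4174 × √0.537 = 0.306

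ANCOVA cuts the M1-only variance by 1 − 0.537 = 46%. The cut is 21% at r = 0.5, 62% at r = 0.8 and 80% at r = 0.9.

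**2. Power** (100,000 simulated trials per row, difference 0.8 SD):

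| r | s | M1 only | Change | ANCOVA |
|---|---|---|---|---|
| 0.5 | 1 | 45% | 45% | 54% |
| 0.7 | 1 | 45% | 66% | 70% |
| 0.8 | 1 | 45% | 82% | 84% |
| 0.9 | 1 | 45% | 98% | 98% |
| 0.7 | 0.8 | 45% | 53% | 70% |
| 0.7 | 1.2 | 45% | 71% | 70% |
| 0.8 | 0.8 | 45% | 69% | 84% |
| 0.8 | 1.2 | 45% | 86% | 84% |

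A separate noncentral-t calculation for s = 1 agrees for M1 only and change. It gives ANCOVA 1 to 2 points more because it leaves out the 20/19 factor. It also shows that at r = 0.3 change is worse than M1 only (34% against 45%). The documents do not say whether 11 is before or after the dropout; with 12 against 10, power is 0 to 3 points lower.

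**3. Type I error.** With one quantity fixed, each method rejects a true null in 4.8–5.1% of trials. If a significant result on either M1 or change could be reported, the rate per outcome is 9.2–9.5% (s = 1, r from 0.5 to 0.9). Over s from 0.8 to 1.5 it runs from 7.8% to 9.8%.

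**4. Chance baseline gap.** A gap between arms above 0.5 SD at M0, in either direction, has probability 2·P(Z > 0.5/0.4174) = 2·P(Z > 1.198) = 0.231 per outcome. For a gap of g M0 SDs, the expected shift in the estimated effect, in M1 SDs, is r·g for M1 only, (r − 1/s)·g for change and 0 for ANCOVA. With g = 0.5 and r = 0.7:

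- M1 only: 0.7 × 0.5 = +0.35
- change, s = 0.8: (0.7 − 1.25) × 0.5 = −0.28
- change, s = 1: (0.7 − 1) × 0.5 = −0.15
- change, s = 1.2: (0.7 − 0.833) × 0.5 = −0.07
- ANCOVA: 0

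Given a gap above 0.5 SD and no true effect, rejection at r = 0.7 and s = 1 is about 14–15% for M1 only, 8% for change and 5% for ANCOVA.

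**The case against.** The strongest reply is that two points of unequal weight are joined here. Not naming the tested quantity is a reporting gap. Not using M0 as a covariate is closer to a preference: if the authors tested change, the test was valid and, with equal SDs and r of 0.7 or more, lost at most about 4 points of power to ANCOVA. With s = 1.2 it gained 1 to 2. One clarifying phrase would then settle most of the matter. This stands in part. It fails if M1 alone was tested, if r is low, or if SDs shrink after training (53% against 70% at r = 0.7, s = 0.8), and the documents rule out none of these.

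The 9% error rate describes conduct that the documents do not report. That is correct: the text leaves it open, but nothing shows that it happened. Likewise, averaged over randomisations, each fixed test keeps its 5% level; the baseline-gap figures apply only once a gap has occurred.

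Every magnitude is assumed, and at r = 0.25 ANCOVA gains nothing over M1 only (45% each). This too is correct. The textual point does not depend on these figures.

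Fisher's exact test suits none of the four continuous outcomes, so the sentence may partly describe baseline characteristics. That is plausible, but it leaves the outcome comparison even less defined.

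Finally, a normal-theory ANCOVA in about 23 people needs a provision for skewed outcomes, since the plan keeps a rank test available. That is fair, and the recommendation below includes one.

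**Conclusion.** The concern holds. As a matter of text, the plan does not say what quantity the between-group tests compare, and no between-group contrast adjusts for M0. The named tests are not invalid, so this is a recommended change rather than a fatal flaw.

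The size depends on which test was used and on r and s, none of them stated. Against M1 only, ANCOVA's gain is large once r reaches 0.7 (at least 25 points of power for a 0.8 SD difference). Against change it is small when SDs are equal and r is 0.7 or more, and large when the M1 SD is the smaller. The case for ANCOVA is robustness: r and s may differ across the four outcomes, and ANCOVA was the best or within about 2 points of the best in every row of the table. It also removes the expected shift from a chance baseline gap. All figures assume normal data and 12 against 11 analysed.

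**What to change.** - State which quantity (M0, M1 or change) the between-group tests were applied to, for each outcome. Label any test at M0 as descriptive.
- For each of the four outcomes, make the comparison of arms an ANCOVA with M1 as response, group as factor and M0 of the same outcome as covariate. Report the adjusted mean difference with its 95% CI.
- Check residuals, and name a rank-based analysis as a sensitivity check for outcomes that are clearly non-normal.
- Present the within-group paired t tests as descriptive, not as evidence that the programmes differ.
- The text is in the past tense. If results have been seen, label the ANCOVA a post hoc reanalysis and report it for all four outcomes beside the tests already run.

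**Cost.** A few sentences, one residual degree of freedom and no new data. If M0 carried no information (r = 0), the 95% CI would be about 3% wider than for M1 only (half-width 0.89 against 0.87 SD). Where change happens to be the better choice (s = 1.2, r of 0.7 to 0.8), about 1 to 2 points of power are given up. Prespecification cannot be restored by a change made after the results are known.

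### Pre-to-post change is explicitly tested only within each arm; the randomised between-arm contrast that the objective needs is left unspecified

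*Combined protocol and SAP*

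**What the plan says.** Study Objectives sets a comparative question: "This study compared a 4-week blood-flow-restriction (BFR) resistance-training program performed at 30% of one-repetition maximum (1RM) with traditional high-load strength training" at 70% of 1RM. Study Design describes a "Parallel-group randomized controlled trial with two intervention arms", with 12 participants in the BFR arm and 11 in the high-load arm after one dropout. Both arms train.

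Methods gives each participant two assessments, M0 before training and M1 at least 24 h after the last session. The only familiarization described is the staff's: "Before data collection, the research team completed a familiarization phase". No participant practice session, run-in or repeat baseline is described.

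Statistical Analysis first names three between-group tests (Fisher's exact, Mann-Whitney U, independent-samples t) without naming the variable they are applied to. It then states: "Within-group pre- to post-changes were evaluated with paired-samples t tests". One significance level, p<0.05, covers everything. Cohen's d is calculated for significant outcomes, without saying which test makes an outcome significant. No baseline-adjusted model, group-by-time term or between-arm difference with a confidence interval is named.

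**The concern.** Change over the four weeks is what the trial is about, and the plan connects change only to the within-arm tests. Two problems follow.

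First, a pair of within-arm p-values is not a comparison of the arms. One can fall below 0.05 and the other above it when the arms do not differ at all. A report that follows the plan could state that only one program improved an outcome, with no test of the difference behind it.

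Second, a within-arm change is not training alone. The seated throw, the isometric lift and the cadence-paced endurance test depend on effort and skill, and participants are people who do no upper-limb strength training. M0 is their first described assessment and M1 their second, so the change may combine training with practice and time. A paired t test cannot separate these. A practice gain common to both arms cancels in the randomised between-arm contrast and nowhere else in this design. Arm circumference is measured with a tape at rest, so the practice argument does not apply to it. The first problem applies to all four outcomes.

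**Working it through.** The documents give no sample size calculation, expected effect, SD or retest shift, so there is no planned figure to reproduce. The calculations below illustrate the size of the problem.

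**Inputs.** n = 12 and n = 11 (Study Design; 3 + 8 = 11 in the high-load arm, so apparently after the dropout). Alpha is 0.05 (Statistical Analysis); the number of sides is not stated, so two-sided is assumed. The true mean change δ, in SDs of the change score, is an assumption and is varied. Changes are taken as normal and the arms as independent.

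**Paired t test in one arm.** The statistic follows a noncentral t distribution with n − 1 degrees of freedom and noncentrality δ√n. The critical values are 2.201 (11 df) and 2.228 (10 df). At δ = 0.5 the noncentralities are 0.5√12 = 1.732 and 0.5√11 = 1.658. Write a and b for the chances of significance at n = 12 and n = 11.

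**Same true change in both arms: chance that exactly one arm is significant.** Formula: a(1 − b) + b(1 − a). At δ = 0.5: 0.353 × 0.677 + 0.323 × 0.647 = 0.448.

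| δ in both arms | a (n=12) | b (n=11) | exactly one significant |
|---|---|---|---|
| 0 | 0.050 | 0.050 | 0.095 |
| 0.2 | 0.097 | 0.092 | 0.172 |
| 0.4 | 0.245 | 0.225 | 0.359 |
| 0.5 | 0.353 | 0.323 | 0.448 |
| 0.6 | 0.475 | 0.436 | 0.497 |
| 0.8 | 0.714 | 0.668 | 0.428 |
| 1.0 | 0.883 | 0.848 | 0.234 |

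The true between-arm difference is zero in every row.

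**Practice gain only, no training effect: chance of at least one significant improvement on an outcome.** Only the upper tail counts, because a significant worsening is not an improvement. Formula: 1 − (1 − a₊)(1 − b₊), where a₊ and b₊ are the upper-tail probabilities.

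| assumed practice gain (SD of change) | a₊ | b₊ | at least one arm |
|---|---|---|---|
| 0 | 0.025 | 0.025 | 1 − 0.975² = 0.049 |
| 0.2 | 0.0925 | 0.0873 | 0.172 |
| 0.3 | 0.156 | 0.145 | 0.279 |
| 0.5 | 0.353 | 0.323 | 0.562 |
| 0.8 | 0.714 | 0.668 | 0.905 |

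Counting significance in either direction would give 1 − 0.95² = 0.0975 in the first row, which is the wrong reference for an improvement.

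**Between-arm t test on change under the same common shift.** In 50,000 simulated trials it rejected in 4.95%, 4.96% and 5.13% at shifts of 0, 0.5 and 0.8 SD, so a common practice gain does not distort it.

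**Precision of that contrast.** There are 21 df, the critical value is 2.080, and the noncentrality is Δ√(12 × 11/23) = 2.396Δ. Power is 21%, 45%, 63% and 78% for Δ = 0.5, 0.8, 1.0 and 1.2 SD of change. It reaches 80% at about Δ = 1.23.

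**The case against.** The plan does contain between-group tests and lists them before the paired tests. It nowhere says that the arms will be compared by which one reached p<0.05, or that the paired tests answer the objective. This stands: the unsupported conclusions are ones the plan permits, not ones it announces. A reader might infer that no between-arm analysis is planned, and the documents do not support that. What they leave open is the variable those tests use.

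A reader might also take the lack of an untrained arm as a design fault. It is not one for this objective, because randomisation between two trained arms supports a comparison of the two programs. Its absence only bars claims that either program worked.

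The practice gain is wholly assumed, and at 0.2 SD each paired test is significant in fewer than 10% of trials. The throw and the lift also had three trials at M0, which gives some exposure within the session. Both points limit how firmly the practice figures can be pressed. Neither affects the first table, which holds whatever produced the common change.

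Finally, a within-arm 95% CI excludes zero exactly when the paired test gives p<0.05, so replacing the tests with such intervals would change little. That is correct, and the fix takes account of it.

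**Conclusion.** The point holds for the standing of the paired tests and for the unspecified between-group analysis. The within-arm tests neither compare the arms nor isolate a training effect, and they are the only analysis the plan explicitly applies to change. Discordant results from identical arms would be common for a common change of 0.4 to 0.8 SD. They are less frequent outside that range (17% at 0.2 SD, 23% at 1.0 SD). The practice figures concern three of the four outcomes and rest on assumed gains, two-sided tests, normal changes and independent arms. Confidence is high in the principle and conditional for the percentages.

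**What to change.** In Statistical Analysis:

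- State that the conclusion for each of the four outcomes rests on the randomised between-arm difference, reported with its 95% CI. Name the estimate: M1 adjusted for M0 by ANCOVA, or the difference in mean change.
- Remove the paired t tests from the inferential analysis. Report within-arm mean changes with their SDs as descriptive, with a note that they may include practice and time effects and are not evidence that either program worked.
- State that the arms will not be compared by which one reached p<0.05.

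This needs no new data, only revised wording and a reanalysis of the existing measurements. Two things are given up. Claims that an arm improved are lost. The remaining contrast, at 12 versus 11, is imprecise, with 80% power only for about 1.23 SD of change. The report should say so, and should not read a non-significant difference as equivalence.

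### Cohen's d is calculated only for significant outcomes, so with 12 versus 11 participants a two-sided between-group t test can yield only d above 0.87, which overstates the effect on average

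*Combined protocol and SAP*

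**What the plan says.** The rule is in the Statistical Analysis section of the combined protocol and SAP: "For significant outcomes, Cohen's d was calculated and interpreted as: very small". Six labels follow: very small (up to 0.20), small (up to 0.50), moderate (up to 0.80), large (up to 1.20), very large (up to 2.00) and huge (above 2.00). The threshold is given as "Statistical significance was set at $p < 0.05", without saying whether tests are one- or two-sided.

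Two kinds of comparison could supply the d:

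- Between groups: "Between-group comparisons used Fisher's exact test, the Mann-Whitney U test, or independent-samples t tests".
- Within groups: "Within-group pre- to post-changes were evaluated with paired-samples t tests".

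The section does not say which of these d belongs to, or which SD is the standardiser. Quantitative variables are summarised as mean and SD "or median (interquartile range), as appropriate". No confidence interval is mentioned for any outcome. Study Design gives 12 participants in the BFR arm and, for the comparator, n = 11 ("3 men, 8 women; one dropout"). The documents contain no sample-size or power calculation.

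**The concern.** An effect size calculated only after a significant test is a selected estimate. In a small trial only large observed differences reach p < 0.05, so the d values that appear are biased upward on average, and most strongly when the true difference is small. That range is plausible here, because both arms receive an active training programme.

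Non-significant outcomes get no effect size and no interval. A reader may then take a non-significant result as evidence that the two methods are equivalent, when the data may be compatible with a sizeable difference in either direction. The trial exists to compare two training methods, so the size and precision of each between-group difference are needed regardless of the p value.

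**Working it through.** The plan gives no minimum d or power figure, so there is nothing of its own to reproduce.

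**Inputs.** From the documents: alpha 0.05; n = 12 and n = 11 (3 + 8 = 11, so 11 reads as the count after the dropout). Assumed: two-sided testing, pooled-SD d, normal data, and a range of true d.

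**Smallest significant between-group d.** Formula: t(0.975, n1 + n2 − 2) × √(1/n1 + 1/n2).

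- 12 vs 11: 2.080 × 0.4174 = 0.868.
- 12 vs 10, or 12 vs 12, if the dropout is counted differently: 0.893 or 0.847.
- 12 vs 11, one-sided: 1.721 × 0.4174 = 0.718.

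Every two-sided value exceeds 0.80, so *very small*, *small* and *moderate* cannot be assigned to a significant two-sided between-group t test.

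**What the cut-off does near the boundary** (95% intervals by inverting the noncentral t, 21 df):

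| Observed d | p | 95% CI | Under the plan |
|---|---|---|---|
| 0.30 | 0.48 | −0.53 to 1.12 | no d |
| 0.80 | 0.069 | −0.06 to 1.64 | no d |
| 0.90 | 0.043 | 0.03 to 1.75 | reported as large |

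The last two rows carry almost the same evidence.

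**Inflation among significant results** (12 vs 11, two-sided t test, 2,000,000 simulated trials per row):

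| True d | Significant | Mean \|d\| if significant | Signed mean if significant | Signed mean ÷ truth | Wrong sign if significant | Mean d, all trials |
|---|---|---|---|---|---|---|
| 0.2 | 7.4% | 1.09 | 0.87 | 4.3 | about 10% | 0.21 |
| 0.3 | 10.5% | 1.10 | 1.02 | 3.4 | 4% | 0.31 |
| 0.5 | 20.8% | 1.15 | 1.14 | 2.3 | 0.5% | 0.52 |
| 0.8 | 44.8% | 1.23 | 1.23 | 1.5 | 0% | 0.83 |
| 1.2 | 78.3% | 1.42 | 1.42 | 1.2 | 0% | 1.25 |

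The last column is what results when d is calculated for every outcome: about 4% above the truth, the usual small-sample bias of d.

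**Paired tests.** If d is standardised by the SD of the change, the threshold is t(0.975, n − 1)/√n: 2.201/√12 = 0.635 and 2.228/√11 = 0.672. If a raw SD is used, with equal pre and post SDs, multiply by √(2(1 − r)), where r is the pre-post correlation (assumed). For n = 12 / 11 this gives 0.49 / 0.52 at r = 0.7 and 0.28 / 0.30 at r = 0.9. Inflation for n = 12, SD of change, mean d if significant against mean d in all trials: 0.90 against 0.54 at true d 0.5; 1.02 against 0.86 at 0.8; 1.62 against 1.61 at 1.5.

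**Mann-Whitney.** With the exact critical U of 33 (two-sided p = 0.044) and shifts of 0.2 to 1.2, |d| is 0.80 or less in about 1–6% of significant results for normal data and 21–35% for lognormal data. Against the 0.868 cut-off the shares are about 2–12% and 30–47%.

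**The case against.** The strongest reply is about scope. The sentence on d directly follows the one on paired tests, so d may be meant for the within-group changes. The 0.87 limit would then not apply: *moderate*, and with a raw SD and high correlation *small*, could be assigned, and for large true changes the filter adds almost nothing. Mann-Whitney results also escape the strict limit. This stands as a limit on the figure of 0.87. It does not remove the selection, which still matters for paired results at moderate true effects and leaves every non-significant outcome without a d.

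Second, group summaries are given whatever the p value, so a reader can often compute d. That holds in part. It works for means and SDs at one time point, poorly for medians, and not for the difference in change if change-score SDs are not tabulated.

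Third, the remedy leaves an already significant d unchanged in this trial; the 4% figure is an average over hypothetical trials. That is correct. The gain is a d for the non-significant outcomes and an interval for all of them, which shows how uncertain a large d is.

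Finally, no test or p value is affected. This also stands, and it keeps the point at the level of reporting.

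**Conclusion.** The concern holds. The plan makes the effect size conditional on significance and provides no interval for any outcome. For a two-sided between-group t test at 12 versus 11, only |d| above 0.868 can be reported. The signed mean of the reported d is then about 4.3 times the truth at a true d of 0.2, 2.3 times at 0.5, 1.5 times at 0.8 and 1.2 times at 1.2.

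These figures rest on two-sided testing, normal data, a pooled-SD d and an assumed range of true effects. The threshold stays above 0.80 if the comparator n is 10 or 12. It is lower for one-sided and paired tests and not strict for Mann-Whitney. This is a reporting weakness that should be fixed; it does not invalidate the tests.

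**What to change.** Remove the condition that limits d to significant outcomes. For all four outcomes (arm circumference, shot-put distance, vertical lift strength and endurance time), report the between-group difference in pre-to-post change in original units and as a standardised effect, each with a 95% confidence interval, whatever the p value. State whether tests are one- or two-sided. Define d, including the SD used as standardiser, separately for between-group and paired results. Use magnitude labels only next to the interval.

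The cost is a change of SAP wording and a few more table cells. It needs no new data and changes no test, so it can be applied to data already collected. The results will look less certain, because the intervals will be wide.

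### Cohen's d is calculated only for significant outcomes, so reported effect sizes are on average selected upward; four outcomes of equal standing are tested at an unadjusted 0.05 with no primary outcome or exploratory label

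*Combined protocol and SAP*

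**What the plan says.** The Study Objectives section compares the two programs "on shoulder muscle strength, power, endurance, and hypertrophy in healthy adults". The Methods section assigns one measure to each domain: "Arm Circumference, Single-Arm Seated Shot-Put Test, Vertical Lift Strength, and Shoulder Endurance Test". Neither section ranks them.

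The Statistical Analysis section gives the tests: "Between-group comparisons used Fisher's exact test, the Mann-Whitney U test, or independent-samples t tests" and "Within-group pre- to post-changes were evaluated with paired-samples t tests". It sets one threshold, "Statistical significance was set at $p < 0.05", and one rule for effect sizes, "For significant outcomes, Cohen's d was calculated and interpreted as", followed by a scale that runs from very small to huge, with large starting above 0.80.

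The plan does not state:
- a primary outcome, a multiplicity rule or an exploratory label;
- confidence intervals;
- whether d belongs to the between-group or the paired tests, or which SD divides it;
- whether the between-group tests use post-training values or change scores.

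**The concern.** There are two separate problems.

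The first is selection. With about a dozen participants per arm, an outcome reaches p < 0.05 only when its observed standardised difference is sizeable. If d is calculated only then, the published values come from the upper part of their sampling distribution, and the remaining outcomes get neither an effect size nor an interval. A missing d may then be read as no difference between BFR and high-load training, which is the question the trial asks.

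The second is multiplicity. Four outcomes of equal standing are each tested at 0.05, so if none truly differs, the chance of at least one significant result exceeds 5%. With no primary outcome and no exploratory label, a reader cannot tell how to weigh a single significant result.

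**Working it through.** The documents give no sample size calculation, power or family-wise error rate, so there is no stated figure to reproduce.

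**Inputs.** From Study Design: "an experimental BFR group ($n = 12$; 3 men, 9 women" and "an active comparator high-load group ($n = 11$; 3 men, 8 women; one dropout". It is unclear whether the 11 is before or after the dropout, so 12 vs 10 was also tried. From Statistical Analysis: alpha 0.05. Assumed: two-sided tests, normal data, and the correlations named below.

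**1. Between-group d on the pooled SD of the tested variable.**
- Smallest |d| that can reach p < 0.05 = t(0.975, 21) × √(1/12 + 1/11) = 2.080 × 0.4174 = 0.868. For 12 vs 10 it is 0.893.
- P(d unreported) = 1 − power from the noncentral t with 21 degrees of freedom. Mean values are by simulation.

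| True d | Power | d unreported | Mean reported \|d\| | Mean d, no filter |
|---|---|---|---|---|
| 0 | 0.050 | 95% | 1.06 | 0.00 |
| 0.5 | 0.208 | 79% | 1.15 | 0.52 |
| 0.8 | 0.448 | 55% | 1.23 | 0.83 |
| 1.5 | 0.929 | 7% | 1.62 | 1.56 |

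The last column shows ordinary small-sample bias. The filter accounts for the gap between the last two columns.

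**2. Paired d on the SD of change.**
- Floor = t(0.975, n − 1)/√n = 2.201/√12 = 0.635 for n = 12, and 2.228/√11 = 0.672 for n = 11.
- True d 0.5: mean reported |d| is 0.90 (n = 12) or 0.95 (n = 11), against 0.54 unfiltered.
- For n = 12, reported against unfiltered: 1.15 and 1.08 at true d 1.0; 1.32 and 1.29 at 1.2; 1.62 and 1.61 at 1.5.

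**3. d on the raw SD.** With equal variances and pre-post correlation r, multiply a change-score floor by √(2(1 − r)). At an assumed r = 0.9 the factor is √0.2 = 0.447:
- paired: 0.635 × 0.447 = 0.284 and 0.672 × 0.447 = 0.300;
- between-group test of change: 0.868 × 0.447 = 0.388.

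At r = 0.5 the factor is 1 and the floors do not move. Mann-Whitney tests have no exact floor.

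**4. Family-wise error.** This assumes one between-group test per outcome and no true difference on any of the four. If the tests are independent, 1 − 0.95⁴ = 0.185. Simulation (12 vs 11, four equicorrelated normal outcomes, 200,000 trials per setting) gives:

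| Assumed correlation | P(any p < 0.05) |
|---|---|
| 0 | 18.6% |
| 0.3 | 17.6% |
| 0.5 | 15.8% |
| 0.7 | 13.3% |
| 0.9 | 9.5% |

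Results for 12 vs 10 are nearly the same. Up to eight within-group tests (four outcomes, two arms) are left out, because no change after training is an unlikely null.

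**The case against.** **Not every reported d need be large.** A reader might infer from the 0.87 floor that the lower grades of the scale can never appear. The documents do not support that. The d sentence directly follows the paired-test sentence, and the scale starts at very small, so a within-group d is at least as plausible. On the raw SD with high pre-post correlation, its floor of 0.28 to 0.30 lies in the small grade. This stands: the upward selection remains, but its size depends on a formula the plan does not give.

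**The bias fades when true effects are big.** This also stands. For paired effects of about 1.2 or more the filter adds little. The documents give no expected effects, so neither case can be ruled out.

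**Readers still have descriptive summaries.** One might infer that the four domains cannot be compared at all. That goes too far, because the plan promises mean and SD, or median and interquartile range. If these are given by arm, a d on post-training values can be derived for outcomes summarised by mean and SD. The summaries are only a partial substitute: they do not give the SD of change, which is needed for a paired d or for an interval on the difference in change.

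**Unadjusted testing can be defended here.** The four measures cover distinct constructs, the plan has no rule that success on any one outcome suffices, and the study is small and in healthy volunteers. Unadjusted per-outcome testing is reasonable if labelled as such. The defect is the missing label and ranking, not the absence of an adjustment in itself.

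**Conclusion.** The concern holds in a conditional form. Calculating d only after significance selects effect sizes upward on average and leaves non-significant outcomes without an effect size or interval. Under the between-group pooled-SD reading, the mean reported value at a true d of 0.5 is about 1.15, and d is missing in 79% of trials. Under the paired reading on the SD of change, it is 0.90 to 0.95 at the same true value, and close to unbiased for true effects of about 1.2 or more. These figures assume normal data and t tests.

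The family-wise rate is 18.6% at correlation 0, 13% to 18% at 0.3 to 0.7, and 9.5% at 0.9. A rate near 10% therefore needs outcomes correlated at close to 0.9, and the documents give no correlations. A reader might take these rates as the probability that a significant finding is false. They are not: each is the chance of any false rejection when no outcome truly differs.

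The change should be made. It corrects reporting and does not call for a redesign.

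**What to change.** Replace the Cohen's d sentence with:

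> For each of the four outcomes, whether or not p < 0.05, the between-group difference in change (M1 minus M0) with its 95% CI is reported, with Cohen's d equal to that difference divided by the pooled baseline SD. For outcomes analysed by Mann-Whitney U, the Hodges-Lehmann difference with 95% CI and the rank-biserial correlation are reported instead. Any within-group d is reported for both arms and all outcomes, with its SD named. Cohen's d is interpreted as: [existing scale].

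Add that no primary outcome was specified, that the four between-group comparisons are exploratory and unadjusted, and how many tests were run.

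Only if a significance claim on BFR versus high-load training is kept, apply Holm across the four between-group tests. Declare it post hoc if data have been seen; the document is in the past tense and already reports a dropout.

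**Cost.** No new data. Full reporting takes table space, and the exploratory label gives up confirmatory claims. Holm, if used, lowers power at d = 0.8 from 45% to as little as 24%, its worst case at the first step (0.05/4 = 0.0125).
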